14.7 Randomization

Following the Protocol version 6.1_UK participants will be randomised in blocks to double-blind treatment in a 1:2 ratio (Placebo : GB0139 3 mg). The unbalanced randomisation is to maintain the same probability of allocation to placebo post-Protocol version 6.1_UK since this may impact participant enrolment. Note that prior to Protocol version 6.1_UK participants were randomized in blocks to double-blind treatment in a 1:1:1 ratio (GB0139 3 mg : GB0139 10 mg : Placebo) stratified by SoC.

The Sponsor will arrange for the randomization and the packaging and labelling of trial medication. The randomization list will be generated using a validated system, which involves a pseudo-random number generator so that the resulting treatment will be both reproducible and non-predictable. The block size will be documented in the CTR. Access to the codes will be controlled and documented.

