### 1.1 Trial design

A randomized, double-blind, multicentre, parallel, placebo-controlled phase 2b study in subjects with idiopathic pulmonary fibrosis (IPF). All subjects enrolled into the study should have a diagnosis of IPF established within the previous five years, and a diagnostic HRCT scan assessed by central independent radiologists according to the ATS/ERS/Fleischner criteria available within the previous 12 months prior to screening.

The original design consisted of 3 treatment groups, placebo, GB0139 3mg and GB0139 10mg, with patients randomized in a 1:1:1 ratio. Stratification in the original version of the study was according to the patient's standard of care treatment at enrollment;

- SoC1 being patients currently treated with either pirfenidone or nintedanib,
- SoC2 being patients not currently treated with pirfenidone or nintedanib.

A subject's SoC must have been deemed as stable by the Principal Investigator or treating physician before their enrollment in the study.

It was initially planned to randomize approximately 450 patients to this design across approximately 70 sites from the European Union and 30 sites from the United States. This design was intended to evaluate the efficacy and safety of GB0139 over 52 weeks of dosing in addition to the subject's current standard of care (SoC) (including treatment with either pirfenidone or nintedanib). It was planned to continue blinded treatment beyond week 52 and up to week 104 to provide further safety follow-up information.

Following a review of unblinded efficacy and safety data by the study's DSMB in February 2021, the study design has been modified based on the DSMB's recommendation. Participants randomized to the 10mg GB0139 group, and all those taking nintedanib or pirfenidone, have been discontinued from the study. In addition, subjects who had already

	Plus-Project Statistical Analysis Plan	
	Protocol Number: GALACTIC-1	Version: 1

completed 52 weeks of treatment were discontinued. In total, about 320 subjects had been randomized under the original design, and approximately 200 were discontinued.

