In the revised version of the study, post the changes following the DSMB recommendations, participants who are not taking nintedanib or pirfenidone at screening and during the study continue in the study. New patients are recruited and randomized to receive either 3mg GB0139 or placebo in a 2:1 ratio, to ensure the same proportion of patients on active drug as in the original design. Approximately 141 patients are expected to be enrolled into the modified design. Both nintedanib and pirfenidone are prohibited in the revised version of the study.

The revised study design consists of a screening period up to 6 weeks, a 52-week double-blind treatment period and a safety follow-up call 7 days post last visit. The duration of the entire trial for each subject will be approximately 59 weeks from first screening to the final safety follow up.

[figure not shown]
After giving Informed Consent, the subject may be selected for the study at Visit 1. Subjects who fail screening may be permitted to undergo re-screening one additional time. If they are successfully re-screened then they will be allocated a new unique subject ID number. If all exclusion and inclusion criteria are fulfilled then randomization occurs at Visit 2 (Week 0). Further visits are scheduled at Week 4 (V3), Week 8 (V4), Week 12 (V5), Week 26 (V6), Week 40 (V7), and Week 52 (V8). Visits 3, 4 and 5 should occur within  $\pm 3$  days of the scheduled time point. Visits 6 and 7 should occur within  $\pm 7$  days of the scheduled time point.

Details for the data collected at each visit are given in the time and events table in Section 11.2.

The revised design is shown in Figure 1 below. For reference, the original design is shown in Section 11.1.

	Plus-Project Statistical Analysis Plan	
	Protocol Number: GALACTIC-1	Version: 1

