## 1.3 Study Populations

There are 3 populations of interest. These are as follows:

[figure not shown]
- **Primary Population** : Subjects recruited under the new design, plus those from the original design recruited to SoC2 (not being treated with nintedanib or pirfenidone prior to screening) and randomized to either placebo or 3mg GB0139.
- **SoC1 Population/Combination**: Subjects recruited under the original design to SoC1 (current treatment at baseline with nintedanib or pirfenidone).
- **SoC2 Population/Monotherapy**: Those subjects from the original design in the SoC2 stratum (not receiving nintedanib or pirfenidone at baseline), plus all subjects from

	Plus-Project Statistical Analysis Plan	
	Protocol Number: GALACTIC-1	Version: 1

the new design. SOC2/Monotherapy Population is the Primary Population plus SoC2 10 mg.

These populations are described visually in Figure 2 below.

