### 3.2 Randomization and Blinding

In the original design, within each SoC subpopulation (SoC1: subjects on nintedanib/pirfenidone at baseline, SoC2: subjects not treated with nintedanib/pirfenidone), subjects were randomized in blocks to double-blind treatment in a 1:1:1 ratio (GB0139 3 mg: GB0139 10 mg: Placebo).

For the updated design, there is no stratification and subjects are randomized in a 2:1 ratio GB0139 3mg: Placebo. The unbalanced randomization is to maintain the same probability of allocation to placebo post design change, since it is considered that this may facilitate participant enrollment.

The Sponsor arranged for the randomization and the packaging and labelling of trial medication. The randomization list will be generated using a validated system, which involves a pseudo-random number generator so that the resulting treatment will be both

	Plus-Project Statistical Analysis Plan	
	Protocol Number: GALACTIC-1	Version: 1

reproducible and non-predictable. The block size will be documented in the Clinical Study Report (CSR). Access to the codes will be controlled and documented.

This study is a double-blind study which will be maintained throughout the study, including the follow up period. The only exception to this is at the point of the design change, when the 10mg group in the SoC2 stratum had to be unblinded in order to withdraw them from the study early. Study medication is identified by a medication code number. Packaging and labelling will be otherwise identical. An Integrated Web Response System (IWRS) will be used to assign subjects to treatment groups at study start. The randomization code will be kept undisclosed up to database lock.

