## **5. GENERAL METHODS AND PRINCIPLES**

The SAP will be finalized and signed-off prior to DBL and unblinding. Any post-hoc analysis (analyses performed post DBL that are different from those described in the final version of the SAP) will be documented in the final clinical study report (CSR) as changes to the planned analysis.

All data collected will be listed, sorted by strata/treatment group, Subject ID, visit and time, with the Primary Population listed first as follows:-

- SoC2/Monotherapy Placebo,
- SoC2/Monotherapy GB0139 3 mg,
- SoC2/Monotherapy GB0139 10mg,
- SoC1/Combination Placebo,
- SoC1/Combination GB0139 3 mg,
- SoC1/Combination GB0139 10mg,
- Screening Failures.

Data on screening failures will be listed only.

Tabulations and data analyses will be performed using SAS® software, version 9.4 or later (SAS Institute, Inc.).

Unless otherwise specified, efficacy analyses will be performed in the mITT Analysis Set, with sensitivity analyses of the primary endpoints and secondary endpoints conducted using the PPS. Safety summaries will be performed using the SS Analysis Set. The ITT Analysis Set will be used to describe demographics, baseline characteristics and medical history.

The populations will be split according to SOC1 / Monotherapy and SOC2 / Combination, as well as per treatment group.

	Plus-Project Statistical Analysis Plan	
	Protocol Number: GALACTIC-1	Version: 1

P-values will be generated for all efficacy treatment comparisons, in all populations, as an exploratory tool for detection of potential contrasts in the material. P-values will not be generated for subgroup analyses.

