### **7.2.3 Key Secondary Efficacy Endpoints Analysis**

For all key secondary endpoints, analyses will be performed in the Primary Population and in the SoC1 / Combination and SoC2 / Monotherapy Populations. As described previously, for the SoC1 / Combination and SoC2 / Monotherapy Populations, endpoints that refer to 52 weeks will in addition consider the 26 week timepoint (where applicable). Subgroup analyses will only be performed for the Primary Population and the SoC1 / Combination Population.

Initial analyses and subgroup analyses will be performed in only the mITT Analysis Set . Kaplan-Meier plots (where applicable) will only be produced for the mITT Set.

#### 7.2.3.1 Proportion of subjects with an absolute decline from baseline in % Predicted FVC of $\leq 10\%$ at Week 52

Spirometry data provided by an external central vendor (Clario/ERT) showing the calculated % Predicted FVC will be used to derive whether the subject showed an absolute decline  $\leq 10\%$  from baseline in predicted %FVC at Week 52.

The superiority of GB0139 3mg compared to Placebo will be tested for the proportion of subjects with an absolute decline  $\leq 10\%$  from baseline in predicted %FVC at week 52.

	Plus-Project Statistical Analysis Plan	
	Protocol Number: GALACTIC-1	Version: 1

The null hypothesis is:

H0: There is no difference in the proportion of subjects with an absolute decline  $\leq 10\%$  from baseline in predicted %FVC between GB0139 3mg and Plc.

The alternative hypothesis is:

Ha: There is a difference in the proportion of subjects with an absolute decline  $\leq 10\%$  from baseline in predicted %FVC between GB0139 3mg and Plc.

A logistic regression model will be fitted with treatment and baseline FVC (mL) included in the model. The Wald test will be used to test for differences between treatments. Odds ratios together with 90% and 95% confidence intervals will be used to quantify the effect of treatment, comparing GB0139 3mg to Placebo as the reference.

Subjects lost to follow-up prior to Week 52 are imputed to have absolute decline  $>10\%$  from baseline in predicted %FVC at Week 52.

The analysis will be repeated by subgroup (separately for each subgroup factor of interest, Section 7.1.1) by adding a fixed effect for the subgroup factor and adding a treatment by subgroup interaction term. The odds ratio between treatments will be assessed within each level of the subgroup.

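### Exploratory 10 mg contrasts in the SoC2/Monotherapy Population rest partly on controls randomised after 10 mg was dropped, with no adjustment for cohort

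*SAP*

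**What the plan says.** **Allocation.** Under the original design, "subjects were randomized in blocks to double-blind treatment in a 1:1:1 ratio" within each SoC stratum (SAP 3.2; Protocol 14.7 agrees). After the February 2021 DSMB review, "Participants randomized to the 10mg GB0139 group, and all those taking nintedanib or pirfenidone, have been discontinued from the study" (SAP 1.1). From then on, "New patients are recruited and randomized to receive either 3mg GB0139 or placebo in a 2:1 ratio" (SAP 1.1).

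**Populations.** SAP 1.3 defines the Primary Population as "Subjects recruited under the new design, plus those from the original design recruited to SoC2" on placebo or 3 mg. It then says that "SOC2/Monotherapy Population is the Primary Population plus SoC2 10 mg". SAP 1.3 also gives the SoC2/Monotherapy outputs an extra treatment arm and column.

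**Analyses.** SAP 7.2.2 and 7.2.2.1 repeat the FVC slope model in this population at 52 and 26 weeks. For the key secondary endpoints, "analyses will be performed in the Primary Population and in the SoC1 / Combination and SoC2 / Monotherapy Populations" (SAP 7.2.3). SAP 5 adds that "P-values will be generated for all efficacy treatment comparisons, in all populations, as an exploratory tool".

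**Adjustment.** The slope model in SAP 7.2.2 contains baseline FVC, time, treatment and treatment-by-time. The key secondary models likewise have no cohort or period term. Nothing limits 10 mg contrasts to concurrently randomised subjects. SAP 9 removes the protocol's subgroup of subjects recruited before versus after version 6.0.

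**The concern.** A placebo or 3 mg subject randomised under the 2:1 design had no chance of receiving 10 mg. Such subjects are properly randomised controls for each other, but not for 10 mg. When they are pooled with the original-design controls, any difference between cohorts in FVC decline or event risk enters the 10 mg effect. This is not the same as pooling cohorts for 3 mg versus placebo, where both arms are present in both cohorts.

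The documents give reasons why the cohorts could differ:

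- **Antifibrotic use.** SAP 4.5 recognises that original-design subjects could start nintedanib or pirfenidone while on randomised treatment. Protocol 8.3.1 now allows this only after study treatment is withdrawn. The main estimand keeps FVC values after initiation (SAP 7.2.2).
- **Entry.** The original design required standard of care to be stable (SAP 1.1). The amended protocol admits patients who have stopped either drug after a short washout (Protocol 8.3.1).
- **Calendar period.** Respiratory hospitalisation counts COVID-19 terms (SAP 7.2.3.3), whose frequency changes over time.

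At stake is the trial's only efficacy information on 10 mg in subjects not on antifibrotics at baseline.

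**Working it through.** **1. The plan's own figures.** With 47 placebo and 94 on 3 mg (141 at 2:1), a difference of 100 mL, SD 240 mL and two-sided alpha 10%, power is 75.4% (SAP 3.1 states 75%). The original design (150 per arm, SD 280 mL, alpha 5%) gives 87.1% (stated 87%). Both reproduce. They do not bear on the concern, but SD 240 mL and the 100 mL design effect are used below.

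**2. Counts.** SoC2 numbers by arm are not given. SAP 1.1 reports about 320 randomised under the original design and about 200 discontinued, leaving about 120. Assume these 120 are original SoC2 placebo and 3 mg subjects split 1:1, so 60 each, with 60 on 10 mg. The figure of 141 is an overall total in Protocol 6.2, but the number enrolled into the modified design in SAP 1.1. Both readings are carried:

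- 141 in total: 141 − 120 = 21 new subjects, so 7 placebo and 14 on 3 mg.
- 141 all new: 47 placebo and 94 on 3 mg.

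**3. Non-concurrent share** = new / (original + new).

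| | 141 in total | 141 all new |
|---|---|---|
| Placebo | 7/67 = 10.4% | 47/107 = 43.9% |
| 3 mg | 14/74 = 18.9% | 94/154 = 61.0% |

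**4. Bias** ≈ share × cohort gap in annual FVC decline. The gap is assumed to be 10 to 50 mL/yr.

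- 10 mg versus placebo: 0.104 × 10 = 1 mL/yr, up to 0.439 × 50 = 22 mL/yr.
- 10 mg versus 3 mg, if tested: 0.189 × 10 = 1.9 mL/yr, up to 0.610 × 50 = 30.5 mL/yr.

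To put the gap on a scale: Protocol 4.1 says the two licensed drugs roughly halve progression, and the synopsis assumes a 200 mL placebo decline, so full-time use is worth about 100 mL/yr. A gap of 10 to 50 mL/yr then corresponds to cohorts differing by 10% to 50% of person-time on these drugs, if that were the only difference.

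**5. Effect on a nominal 10% test** (normal approximation). SE = 240 × √(1/60 + 1/placebo n). Rejection rate under no true effect = Φ(−1.645 + bias/SE) + Φ(−1.645 − bias/SE). At a 50 mL/yr gap:

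- 67 placebo: SE 42.7, bias 5.2, rejection 10.3%.
- 107 placebo: SE 38.7, bias 22.0, rejection 15.4%.

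**6. Sensitivity to the counts.** Let original SoC2 placebo plus 3 mg range from 30 to 120, with the 10 mg arm half that number. The non-concurrent placebo share then runs from 10% to 76%. A 50 mL/yr gap gives a bias of about 5 to 38 mL and a rejection rate of 10% to 16%. With no gap there is no bias.

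**7. Precision lost with concurrent controls only.**

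| Original placebo n | SE, concurrent only (mL) | SE, pooled (mL) |
|---|---|---|
| 60 | 43.8 | 38.7 to 42.7 |
| 30 | 62.0 | 51.7 to 54.1 |

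**The case against.** **No formal conclusion depends on these contrasts.** The amended hypotheses concern 3 mg versus placebo, the Primary Population has no 10 mg arm, and SAP 5 labels the p-values exploratory. In the SoC2/Monotherapy Population the other secondary endpoints are descriptive only (SAP 7.2.4). This stands and limits the weight of the point. It does not answer it, because an exploratory label does not remove confounding from an estimate.

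**The redesign itself.** A reader might infer that the evidence behind dropping 10 mg is compromised. The documents do not support that: the DSMB review came before any subject was randomised under the revised design.

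**10 mg versus 3 mg.** A reader might take this as a planned test. The written hypotheses and the SAS code in SAP 11.5.1 cover only 3 mg versus placebo. The dose contrast is reached only through the general wording of SAP 5.

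**The numbers are assumptions.** This stands. The figure of 60 is weak because subjects who had completed 52 weeks were also among the roughly 200 discontinued (SAP 1.1), yet SoC2 completers still belong to this population. The size and direction of the cohort gap have no source in the documents.

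**Concurrent controls do not make the comparison clean.** This also stands. The 10 mg SoC2 subjects were unblinded and withdrawn early (SAP 3.2), while eligible placebo and 3 mg subjects continued under the amended protocol (Protocol 10.3.3.1). Restriction by randomisation period alone leaves that imbalance.

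**The mix will be visible.** SAP 1.3 plans a composition table by population, part and treatment group. That shows the mix but does not adjust any estimate.

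**Conclusion.** The point holds for the exploratory 10 mg comparisons on the primary and key secondary endpoints in the SoC2/Monotherapy Population. They are partly confounded with cohort, and the SAP has neither a period term nor a restriction to concurrent controls. The same applies to 10 mg versus 3 mg if that contrast is produced under SAP 5, with a larger non-concurrent share (19% to 61%, against 10% to 44% for placebo on the same assumptions).

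The illustrative bias in 10 mg versus placebo is about 1 to 22 mL/yr, against a 100 mL design effect. It rests on 60 original placebo subjects, 7 to 47 later ones and a gap of 10 to 50 mL/yr, none of which can be confirmed from the documents. The low end is negligible. The high end is a little over half a standard error (22.0/38.7 = 0.57). A reader might conclude that the 10 mg results cannot be interpreted at all, but these figures do not support that. Nor are the later controls non-randomised in general: they were randomised, but not against 10 mg. The primary 3 mg versus placebo analysis is unaffected. The change is worth making because it is cheap, but it is not essential to the trial's main conclusion.

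**What to change.** In SAP 1.3, 7.2.2.1 and 7.2.3, state that every contrast involving 10 mg uses only SoC2 subjects randomised under the original 1:1:1 design.

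If later subjects are kept in the same model, add design period, with period-by-time in the slope model, period-by-visit in the MMRM, and a period main effect in the logistic and Cox models. State that this assumes the cohort difference is the same on placebo and 3 mg, since 10 mg exists in one period only.

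Also state that 10 mg follow-up is truncated relative to continuing controls because of the early unblinding and withdrawal. Name the 26-week contrast, or an analysis of data up to the design change, as the main 10 mg comparison. Present the 52-week 10 mg results as secondary to it.

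The cost is SAP wording and one population flag before database lock, plus somewhat wider intervals for the exploratory 10 mg contrasts. At 60 per arm the SE would be about 44 mL instead of 39 to 43 mL, and at 30 per arm about 62 mL instead of 52 to 54 mL. The Primary Population analysis does not change.

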**Figure 2: Populations for analysis**

Randomized treatment and randomization strata will be identified per the randomization schedule post-unblinding.

Unless otherwise stated, all analyses will be conducted in the Primary Population. Analysis will be repeated in the SoC1 / Combination and / or SoC2 / Monotherapy Population where specified. For the SoC1 / Combination and SoC2 / Monotherapy Populations, there is an additional treatment arm and therefore an extra column will be displayed in the corresponding outputs.

A summary table showing the composition of the three populations by population, part and treatment group will be provided.

For further details on selection of subjects for analysis, see Section 4, Analysis Sets.

## 2. STUDY OBJECTIVES AND OUTCOME MEASURES

Primary and key secondary endpoints that refer to the 52 week timepoint will also be analyzed at the 26 week timepoint for the SoC1 /Combination and SoC2 / Monotherapy Populations.

	Plus-Project Statistical Analysis Plan	
	Protocol Number: GALACTIC-1	Version: 1

## 2.1 Primary Efficacy Objective and Outcome Measures

Primary Efficacy Objective:	Primary Outcome Measures:
To evaluate the effect of GB0139 dry powder for inhalation compared with placebo over 52 weeks treatment period on the annual rate of decline in FVC in participants with IPF who are not treated with or cannot tolerate nintedanib or pirfenidone.	The annual rate of decline in Forced Vital Capacity (FVC; expressed in mL over 52 weeks) in those receiving 3mg or placebo and who are not being treated with nintedanib or pirfenidone.

## 2.2 Secondary Objectives and Outcome Measures

Secondary Efficacy Objective:	Key Secondary Outcome Measure:
To further characterize the effect of GB0139 compared with placebo over 52 weeks treatment period on FVC, quality of life, time to respiratory-related hospitalizations and all-cause mortality.	Proportion of subjects with an absolute decline from baseline in FVC (% pred) of $\leq 10\%$ at Week 52.
	
Change from baseline in St George's Respiratory Questionnaire (SGRQ) total score at Week 52.
 
Time to first hospitalization (respiratory related, including acute exacerbation of IPF).
 
Time to death (all causes).

	Other secondary outcome measures:
	Proportion of subjects with an absolute decline from baseline in FVC (% pred) of $\leq 5\%$ at week 52.
	Change from baseline in 6-minute walk test (6MWT) distance over 52 weeks.
	Change from baseline in diffusion capacity of the lung for carbon monoxide (DLCO), corrected for HB, over 52 weeks.
	Change from baseline at week 52 for dyspnea assessment by University of

	Plus-Project Statistical Analysis Plan	
	Protocol Number: GALACTIC-1	Version: 1

	
California San Diego - Shortness of Breath Questionnaire (UCSD - SOBQ).
 
Change from baseline at week 52 for HRQoL as assessed by Short Form Survey (SF-36).
 
Percentage of subjects with Adverse Events (AE) or Serious Adverse Events (SAE).
 
Time to first hospitalization (IPF related, including acute exacerbation of IPF).
 
Time to first hospitalization (all cause).
 
Time to respiratory-related death.
 
Change in FVC expressed in mL over 52 weeks for subjects who have never been treated with pirfenidone or nintedanib. [a]

--	--

[a] Only to be considered for the Primary and the SoC2 / Monotherapy Population.

